#### 4.4 END OF STUDY DEFINITION

The Le Rêve 3.0 study will span 12 weeks in time (for Schema see section 1.2). The end of data collection for Le Rêve 3.0 will be defined as the last day of drug washout on the seventh day of the twelfth week.

### 5 STUDY POPULATION

#### 5.1 INCLUSION CRITERIA

In order to be eligible to participate in this study, an individual must meet all of the following criteria:

- 1) Has provided a signed and dated informed consent form.
- 2) Presence of chronic insomnia defined as self-reported difficulty initiating (latency to persistent sleep >30 min) and/or maintaining sleep (>30 mins awake during the middle of the night, or waking >30 mins before desired waking time on three or more nights per week) for at least 3 months.
- 3) Insomnia Severity Index score >15.
- 4) Male or female aged 25–70 years.
- 5) Is willing to comply with *all* study procedures throughout the entire study, including:
  - Wearing a sleep-tracking device on their wrist throughout entire clinical study.
  - Ensuring that the sleep-tracking device is connected to their smartphone via Bluetooth on a daily basis so that sleep data can be collected on a daily basis.
  - Ensuring that the sleep-tracking device is charged before going to bed each night, ensuring that sleep data can be collected on a daily basis.
  - Is willing to receive and respond to daily text (SMS) notifications for the duration of the entire clinical study.
  - During the treatment phases of the study, is willing to take the treatment for at least four nights in each week.
- 6) On the nights in which the participant takes the treatment, is willing to abstain from excessive alcohol intake (>two drinks/day).

7) On the nights in which the participant takes the treatment, is willing to refrain from drinking alcohol two hours before bedtime.

8) Female subjects who:

-Are postmenopausal, with amenorrhea for at least one year before the screening interview, OR

-Are surgically sterile, OR

-If of childbearing potential agree to practice effective double barrier methods of contraception (e.g., condom + diaphragm; condom or diaphragm + spermicidal gel or foam), from the time of the signing of informed consent through the last dose of study treatment, or agree to completely abstain from intercourse.

9) Self-reported bedtime between 9 pm and midnight on four-seven nights per week.

10) Owns a smartphone.

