## 1.2 SCHEMA

### 1.3 SCHEDULE OF ACTIVITIES (SOA)

Procedures	Screening Weeks -4 to -1	Enrollment Day 1	Collect Baseline Data Weeks 1-2	Treatment 1 Weeks 3-6	Treatment Washout Week 7	Treatment 2 Weeks 8-11	Treatment Washout Week 12	Post-Treatment Weeks 13-20
Informed consent	X							
Medical history	X							
Randomization				X				
Administer study intervention				X		X		
Adverse event review and evaluation								X

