## 4 STUDY DESIGN

### 4.1 OVERALL DESIGN

We hypothesize that Defined CBD, a novel CBD-based formulation in the form of a small orally administered capsule, will increase the percentage of time participants spend in deep (SWS) and REM sleep, as measured by an objective sleep-tracking device called “Whoop”. Our research study, entitled Le Rêve 3.0, is a double-blind, placebo-controlled, randomized, crossover investigational study to determine if Defined CBD, a Custom-Formulated CBD Capsule, influences sleep physiology. This capsule contains no Δ-9-THC. As this study is only designed to evaluate the effects of Defined CBD on the structure and function of sleep physiology, the phase of the trial is not applicable. This trial is not intended to treat, diagnose, prevent, or cure any disease.

The Le Rêve 3.0 study will involve a cross-over design in which study participants will cycle through two independent treatments, each for four weeks (Treatment 1: Placebo; Treatment 2: Defined CBD). The placebo will look, smell and taste the same as the Defined CBD capsule. The study participants will initially be randomized with respect to the treatment arm, and every participant will cycle through both treatment arms. We will use a double-blind design in which the investigator and study participants will both be blinded to the treatments. Baseline data for each participant will be collected for two weeks prior to initiating treatments, as well as for a one-week washout period following each treatment arm. The entire study duration will be 12 weeks (for Schema see section 1.2).

Primary data for Le Rêve will be obtained in a completely unbiased manner from a non-invasive sleep-tracking wrist-worn device called “Whoop” (<https://www.whoop.com>), that electronically collects and transmits sleep data from study participants in the comfort of their own beds.

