- 19) Inability to refrain from use of any of the following contra-indicated drugs for at least one week prior to and for the duration of the study: erythromycin, clarithromycin, itraconazole, ketoconazole, posaconazole, voriconazole, ritonavir, telaprevir, boceprevir, amlodipine, gemfibrozil, cyclosporine, danazol, amiodarone, verapamil, diltiazem, rifampin, theophylline, tizanidine, bupropion, efavirenz, diflunisal, propofol, fenofibrate, lamotrigine, morphine, lorazepam, diazepam, clobazam, stiripentol, valproate, everolimus, sirolimus, or tacrolimus, niacin (vitamin B3 greater than 1g/ day), grapefruit juice.
- 20) Consumption of xanthine-containing beverages (i.e., tea, coffee, energy drinks or cola) of more than five cups or glasses per day.
- 21) Inability to refrain from greater than 400mg/day of caffeine consumption for study duration.
- 22) Participation in any other clinical trial within 30 days before the screening visit.
- 23) Night shift workers (during the 12 months prior to the study and during the study).
- 24) Individuals who nap three or more times per week over the preceding month.
- 25) Current delayed sleep phase syndrome where wake-up time is regularly (>5x/week) later than 9:00 a.m.
- 26) Individuals having to travel across more than two time zones or outside of their country of residence at any time during the study.
- 27) Females who are pregnant, are planning to become pregnant, or are breastfeeding.

28) History of allergies particularly to plant-based products containing terpenes, i.e. flavors and aromatic natural oils for example citrus, mango, lavender, thyme, cedarwood and pine products.

29) Known hypersensitivity to cannabinoids, including CBD.

30) Individuals may be excluded from participating in the study based on the investigator's professional judgement.

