### 6.3 MEASURES TO MINIMIZE BIAS: RANDOMIZATION AND BLINDING

After enrollment, study participants will be assigned a study participant number, and will be randomized to receive Defined CBD or the Placebo control first. As Le Rêve 3.0 is a crossover study, participants who are randomized to receive Defined CBD as the first treatment will cross-over to receive the Placebo Control as the second treatment, and vice-versa. Both the study participants and the PI will be blinded to the study treatments. Unblinding will occur at the completion of the study by the PI. In certain rare instances (e.g. for a SAE), the blind may be broken for an individual participant by the PI.

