### 8.3.4 TIME PERIOD AND FREQUENCY FOR EVENT ASSESSMENT AND FOLLOW-UP

The occurrence of an AE or SAE may come to the attention of study personnel during interviews of a study participant presenting for medical care, or upon review by a study monitor.

All AEs including local and systemic reactions not meeting the criteria for SAEs will be captured on the appropriate electronic case report form (eCRF). Information to be collected includes event description, time of onset, medical monitor's assessment of severity, relationship to study product, and time of resolution/stabilization of the event. All AEs occurring while on study must be documented appropriately regardless of relationship. All AEs will be followed to adequate resolution.

Any medical condition that is present at the time that the participant is screened will be considered as baseline and not reported as an AE. However, if the study participant's baseline medical condition worsens at any time during the study, it will be recorded as an AE.

Changes in the severity of an AE will be documented to allow an assessment of the duration of the event at each level of severity to be performed. AEs characterized as intermittent require documentation of onset and duration of each episode.

The medical monitor will record all reportable events (AEs and SAEs) starting with the first day of the study until the study is completed. The medical monitor will follow up with the study participant up to three times until resolution or stabilization.

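### Inclusion 8 ends double-barrier contraception at the last dose, leaving barrier users whose last dose is CBD with no required cover in the final washout week

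*Combined protocol and SAP*

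**What the plan says.** Section 5.1, inclusion 8, admits women who are postmenopausal, surgically sterile or, if of childbearing potential, willing to use double-barrier contraception "from the time of the signing of informed consent through the last dose of study treatment". Complete abstinence is the alternative, and it carries no end date of its own.

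Section 1.3 places Treatment 2 in weeks 8-11 and then lists "Treatment Washout Week 12". Section 4.4 ends data collection on "the last day of drug washout on the seventh day of the twelfth week". Section 4.1 says "The entire study duration will be 12 weeks" and puts a one-week washout after each treatment.

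Under section 6.3, participants randomized to placebo first take CBD second, and the reverse. The same section states: "Both the study participants and the PI will be blinded to the study treatments". Section 6.1.2 has the capsules taken one hour before bedtime on at least four nights a week.

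Elsewhere, exclusion 27 (section 5.2) bars "Females who are pregnant, are planning to become pregnant, or are breastfeeding". The lifestyle rules in section 5.3 do not mention contraception, and section 8.3.9 marks pregnancy reporting as not applicable.

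**The concern.** The sponsor judged contraception necessary while women are taking study treatment. The requirement then stops at the last dose, just before a week that section 4.4 describes as a washout of drug. If that week exists because CBD may still be present, the reason for requiring contraception has not ended when the requirement does.

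The timing of the dose sharpens this. The capsules are taken shortly before bed to act on that night's sleep. Read literally, inclusion 8 lapses once the final capsules are swallowed, so that same night already falls outside it.

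The rule also protects the two sequences unequally. A woman who completes CBD then placebo is covered well past her last CBD dose, because the requirement follows the last dose of either treatment. A woman who completes placebo then CBD has no cover after hers. What is at stake is unintended conception during any residual exposure. The efficacy analysis is not involved.

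**Working it through.** The plan states no figure for this interval, so there is none to reproduce. The check is a calendar comparison.

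**Inputs**
- Periods (sections 1.3 and 4.1): baseline weeks 1-2, Treatment 1 weeks 3-6, washout week 7, Treatment 2 weeks 8-11, washout week 12.
- Minimum dosing (section 6.1.2): four nights per week.
- End of the contraception requirement (inclusion 8): day of the last dose of either treatment.

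**Calendar.** Week w covers days 7(w − 1) + 1 to 7w. The periods sum to 2 + 4 + 1 + 4 + 1 = 12 weeks, which agrees with section 4.1.
- Treatment 1: days 15-42
- Week 7 washout: days 43-49
- Treatment 2: days 50-77
- Final washout: days 78-84

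**Placebo then CBD, completer.** Uncovered days = 84 − day of last dose.
- Last dose on the final night of week 11 (day 77): 84 − 77 = 7 days.
- Four doses on the first four nights of week 11 (days 71-74), which is still compliant: 84 − 74 = 10 days.

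**CBD then placebo, completer.** The last CBD dose is on day 42 at the latest, and the requirement runs to the last placebo dose, on day 74 at the earliest if dosing is compliant. Cover after CBD is therefore at least 74 − 42 = 32 days, which includes the whole of week 7. She has no post-CBD gap.

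**Stopping early on CBD, either sequence.** If the last dose is on day d, required cover after day d is 0, against the protocol's own 7-day washout length.

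**Does another rule fill the gap?** Exclusion 27 removes women planning pregnancy but sets no contraception period and does not address unplanned conception. Section 5.3 is silent on contraception. Nothing in the protocol text available extends the barrier requirement past the last dose.

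**Who is affected.** Only women of childbearing potential who use the barrier option and whose last dose is CBD. With 1:1 allocation (an assumption, since the ratio is not stated), the placebo-first sequence would hold about half of the women of childbearing potential. Their number is not given.

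**The case against.** The strongest reply is that no harm is shown. The documents contain no half-life, reproductive-toxicity or fetal-risk data. In a crossover, a washout may serve only to separate treatment periods for the outcome, and section 4.1 presents these weeks mainly as a time of data collection. Whether cover is needed after dosing, and for how long, is then a pharmacological question outside the documents. This stands as a limit on the size of the point. It does not remove the zero post-dose cover, and some exposure on the night of the last dose follows from the trial's own premise.

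A second reply is that rules with different purposes may end at different times. A reader might infer that the protocol contradicts itself, because exclusion 19 bars "contra-indicated drugs for at least one week prior to and for the duration of the study" and section 8.3.4 has adverse events recorded "starting with the first day of the study until the study is completed". The documents do not support that reading. Section 2.3.1 presents the drug restriction as a precaution concerning liver function, and event recording is ordinary follow-up. The schedule in section 1.3 marks adverse event review in weeks 13-20, so recording is not shown to stop on day 84. Inclusions 6 and 7 tie alcohol rules to treatment nights, so linking a rule to dosing is not unusual in this protocol.

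A reader might also infer that the blind makes it impossible to know who took CBD last. Section 6.3 lets the investigator break an individual blind in rare cases and unblinds at completion. Blinding is a good reason for a uniform rule, but no more than that.

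Finally, the consent form was not available. Section 10.1.1.1 says it describes procedures and risks in detail, so it may set a longer period.

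**Conclusion.** The point holds as a minor participant-safety matter. Barrier users whose last dose is CBD have no required contraception after it. For placebo-then-CBD completers this leaves 7 to 10 days uncovered up to the end of washout, assuming compliant dosing in week 11. For women who stop early on CBD, required cover after the last dose is 0 days.

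Two stronger readings should be avoided. The first is that every completer has a week of unprotected CBD exposure: CBD-then-placebo completers do not, the abstinence option has no stated end date, and postmenopausal and surgically sterile women are outside the rule. The second is that the fetus is at risk for 7 days: that figure is the protocol's washout length, not a pharmacological estimate, and the documents do not allow the risk to be sized. Sample size, power and the primary analysis are unaffected.

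**What to change.** Amend inclusion 8 so that women of childbearing potential agree to double-barrier contraception or abstinence from consent through the end of the final washout (week 12, day 7). If treatment stops early, require it for at least 7 days after the last dose. Let the medical monitor set a longer period where judged necessary, since 7 days is only the protocol's own washout length. Apply the rule to all women of childbearing potential because treatment is blinded, give both options the same end date, and align the consent form if it differs.

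With this change, uncovered time within the study falls to 0 days for completers. The cost is one protocol line, possibly a matching consent line, and about one extra week of contraception or abstinence, including for women whose last dose was placebo. No visits or tests are added.

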## 5.2 EXCLUSION CRITERIA

An individual who meets any of the following criteria will be excluded from participation in this study:

1) Self-reported body mass index > 32 calculated from patient's height (m) and weight (kg); weight (kg)/square height ( $m^2$ ).

2) Insomnia associated with clinically diagnosed sleep apnea (AHI greater than 15 events/hour), or movement disorders such as restless legs, periodic limb movement (PLM) (greater than 30 events/hour or greater than five events/hour with associated PLM arousals).

3) Are currently participating in a formal behavioral therapy program to facilitate sleep.

4) History of epilepsy or seizures.

5) History of liver disease.

6) Serious head injury or stroke within the past year.

7) Psychiatric disorders including major depression, bipolar, anxiety, or schizophrenia.

8) History of suicide attempt or current suicide ideation.

9) Evidence of any clinically significant, severe or unstable, acute or chronically progressive medical or surgical disorder (including planned medical procedures that may impact sleep), or any condition that may interfere with the absorption, metabolism, distribution, or excretion of the study drug.

10) Patients with a history of cardiovascular disease including poorly controlled hypertension, ischemic heart disease, arrhythmia, or severe heart failure.

- 11) Untreated metabolic disorder such as diabetes.
- 12) Medical conditions that result in frequent need to get out of bed (e.g. nocturia).
- 13) History of drug or alcohol abuse, including past or present history of cannabis dependence.
- 14) Inability to refrain from greater than two standard drinks/day of alcohol consumption for study duration.
- 15) Current cigarette smoker.
- 16) Currently chronic (daily) cannabis user.
- 17) Use of any substance with psychotropic effects or properties known to affect sleep/wake, including neuroleptics, morphine/opioid derivatives, antihistamines, stimulants, anti-depressants, clonidine, within one week prior to screening.
- 18) Use of any over-the-counter sleep medications including tryptophan, valerian root (*Valeriana officinalis*), kava (*Piper methysticum* Forst), melatonin, St John's Wort (*Hypericum perforatum*), Alluna (herbal sleep supplement with valerian root), and hemp within one week prior to screening.
- 19) Inability to refrain from use of any of the following contra-indicated drugs for at least one week prior to and for the duration of the study: erythromycin, clarithromycin, itraconazole, ketoconazole, posaconazole, voriconazole, ritonavir, telaprevir, boceprevir, amlodipine, gemfibrozil, cyclosporine, danazol, amiodarone, verapamil, diltiazem, rifampin, theophylline, tizanidine, bupropion, efavirenz, diflunisal, propofol, fenofibrate, lamotrigine, morphine, lorazepam, diazepam, clobazam, stiripentol, valproate, everolimus, sirolimus, or tacrolimus, niacin (vitamin B3 greater than 1g/ day), grapefruit juice.
- 20) Consumption of xanthine-containing beverages (i.e., tea, coffee, energy drinks or cola) of more than five cups or glasses per day.
- 21) Inability to refrain from greater than 400mg/day of caffeine consumption for study duration.
- 22) Participation in any other clinical trial within 30 days before the screening visit.
- 23) Night shift workers (during the 12 months prior to the study and during the study).
- 24) Individuals who nap three or more times per week over the preceding month.
- 25) Current delayed sleep phase syndrome where wake-up time is regularly (>5x/week) later than 9:00 a.m.
- 26) Individuals having to travel across more than two time zones or outside of their country of residence at any time during the study.
- 27) Females who are pregnant, are planning to become pregnant, or are breastfeeding.

28) History of allergies particularly to plant-based products containing terpenes, i.e. flavors and aromatic natural oils for example citrus, mango, lavender, thyme, cedarwood and pine products.

29) Known hypersensitivity to cannabinoids, including CBD.

30) Individuals may be excluded from participating in the study based on the investigator's professional judgement.

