### 5.3 LIFESTYLE CONSIDERATIONS

During this study, participants are asked to:

- Refrain from ingesting greater than two standard drinks/day of alcohol consumption for study duration.
- Refrain from drinking alcohol two hours before bedtime.
- Abstain from ingesting greater than 400 mg/day of caffeine consumption for study duration.
- Abstain from ingesting caffeine after 3 pm for study duration.
- Abstain from ingesting more than five cups or glasses per day of xanthine-containing beverages (i.e., tea, coffee, energy drinks or cola) for study duration.

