#### 6.2.2 FORMULATION, APPEARANCE, PACKAGING, AND LABELING

The treatments will come in two independent blister packs labeled “Defined Research Treatment 1” and “Defined Research Treatment 2”. The blister packs contain a sufficient number of capsules for a total of 28 days of treatment (either Defined CBD or the Placebo Control).

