## 6.5 CONCOMITANT THERAPY

Not applicable.

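### Exclusion criteria 17 and 18 stop at screening, so the protocol text permits OTC sleep aids, hemp, non-daily cannabis and own CBD in both treatment phases and describes no planned record of them

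*Combined protocol and SAP*

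**What the plan says.** Section 5.2 contains two kinds of substance rule.

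- **Entry-only rules.** Criterion 17 covers "Use of any substance with psychotropic effects or properties known to affect sleep/wake", and criterion 18 covers OTC sleep products, closing with "Alluna (herbal sleep supplement with valerian root), and hemp within one week prior to screening". Both look back one week from screening. Cannabis is also limited by criterion 13, "History of drug or alcohol abuse, including past or present history of cannabis dependence", and by criterion 16, which excludes current daily users. Both describe a person's history or status at entry.
- **Rules that continue on study.** Criterion 19 lists contra-indicated drugs to be avoided "for at least one week prior to and for the duration of the study". Sections 2.3.1 and 8.2.4 repeat the requirement. Section 5.3 adds limits on alcohol, caffeine and xanthine drinks, for example "Abstain from ingesting caffeine after 3 pm for study duration".

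Section 6.5, on concomitant therapy, reads "Not applicable", as does 6.5.1 on rescue medicine. The daily text message is described in 6.4 as confirming whether the study capsules were taken, and in 10.1.7 as serving compliance and the capture of adverse events.

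**The concern.** The sponsor regarded melatonin, valerian, kava and hemp as important enough to exclude recent users, but the exclusion lapses before anyone is treated. Caffeine in the late afternoon is restricted throughout the study; the participant's own supply of the trial's active ingredient is not.

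The people enrolled have an Insomnia Severity Index above 15, sleep at home, spend four weeks on placebo and have no rescue medicine. If some of them take CBD during the placebo phase, the placebo period is no longer free of CBD and the primary contrast shrinks. If other sleep aids are used more in one phase than in the other, the contrast can be biased, and the documents do not establish in which direction. Without a planned record, the analysis would have little on which to judge whether either had happened.

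**Working it through.** **1. Timing of the criteria 17 and 18 window.** Inputs are from section 1.3: "Screening Weeks -4 to -1", baseline in weeks 1-2, Treatment 1 in weeks 3-6, Treatment 2 in weeks 8-11. I assume there is no week 0.

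- Screened at the start of week -4: weeks -4, -3, -2, -1, 1 and 2 pass before dosing, which is 6 weeks. The end of Treatment 2 comes 4 + 11 = 15 weeks after screening.
- Screened at the end of week -1: weeks 1 and 2 pass before dosing, which is 2 weeks. The end of Treatment 2 comes 11 weeks after screening.

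**2. What binds during treatment.**

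| Substance | Entry rule | On-study rule |
|---|---|---|
| Morphine, lorazepam, diazepam, clobazam, bupropion, tizanidine | Criterion 19 (some also under 17) | Yes, criterion 19 |
| Alcohol, caffeine, xanthine drinks | Criteria 6, 7, 14, 20, 21 | Yes, section 5.3 |
| Melatonin, valerian, kava, other OTC sleep aids | Criterion 18 | None stated |
| Hemp | Criterion 18 | None stated |
| Cannabis | Criteria 13, 16 and, on its face, 17 | None stated |
| Participant's own CBD | Not named; hemp-derived CBD arguably under 18 | None stated |
| Antihistamines and other criterion 17 drugs not in 19 | Criterion 17 | None stated |

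**3. What would be recorded.** Sections 6.4 and 10.1.7 describe the text messages without any question on other products. The survey in 8.1 concerns perceived treatment effect. Abuse and misuse in 8.3.8 refer to the investigational product. Section 10.1.10 defines a deviation as failure to comply with the protocol or GCP. With no rule against melatonin in week 5, taking it does not breach the protocol, so the deviation process has no reason to log it.

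**4. Opportunity.** Each pack holds a "sufficient number of capsules for a total of 28 days of treatment", so two packs cover 2 x 28 = 56 nights. Section 6.1.2 requires at least four nights a week, that is 4 x 4 x 2 = 32. A fully compliant participant may therefore go 56 - 32 = 24 treatment-phase nights without a study capsule. This shows room for other products, not how often they would be used.

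**5. Effect on the contrast.** Let D be the true CBD-placebo difference without outside products.

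- *Own CBD.* If a share c of participants loses a fraction f of its contrast, the expected mean difference becomes D x (1 - c x f). With equal use in both phases, a user's contrast is effect(own + 300 mg) minus effect(own). That is smaller than effect(300 mg) minus effect(0) if the response flattens with dose, and equal to it only if doses add without loss.
- *Another sleep aid with additive effect s.* If it is used on a proportion u1 of nights under CBD and u0 under placebo, the contrast becomes D + s x (u1 - u0). Equal use gives u1 - u0 = 0 and cancels.

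The documents give none of c, f, s, u1 or u0. Section 9.2 states power without an SD. Its enrolment figure does reproduce: 100 / (1 - 0.33) = 149.3, rounded up to 150. That covers dropout and says nothing about dilution.

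**The case against.** The strongest reply is the design. Participants and the investigator are blinded, order is randomized, and each person is their own control. Nobody can knowingly choose the placebo phase for their own CBD, and steady use of other sleep aids largely cancels. Entry criteria also remove recent users of sleep aids and hemp, daily cannabis users and people with drug abuse or cannabis dependence. This stands, and it limits the concern about other sleep aids to use that differs by phase. It does not cure own CBD, which can reduce the contrast even when used equally in both phases.

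The evidence on recording is also limited. A reader might infer from the Schedule of Activities, which has no row for concomitant products, that nothing will be captured. That table also omits the Whoop recording, the daily texts and the survey, all of which are planned, so its silence shows little. The adverse event fields in 8.3.4 are introduced as inclusions, and 10.1.7 does not give the text questions in full. Section 6.5 may be an unfilled template heading, since criterion 19 plainly does restrict concomitant drugs. What can be said is that no planned recording is described. That the sponsor could never show what happened does not follow: the consent form (10.1.1.1) and call script (5.4) were not available and may carry instructions.

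A reader might also turn the survey figures in section 2.2 (about 14% of US adults using CBD; about 45% of adults who had tried it using it for sleep) into a contamination rate or a loss of power. The documents do not support that. The figures describe other populations, and this trial screens out recent hemp users. They show that the behavior is foreseeable and no more.

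The general duty to follow study procedures (criterion 5) and withdrawal for non-compliance (7.2) name none of these products.

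**Conclusion.** The point holds on the protocol text. A rule exists, but its time window ends about 2 to 6 weeks before the first dose, while neighboring rules run through the study. OTC sleep aids, hemp, non-daily cannabis and own CBD are therefore permitted in both treatment phases, and no planned recording of them is described.

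The size of any dilution or bias cannot be estimated. That the window covers no treatment nights follows from its wording and does not measure harm. The dilution argument assumes that some participants use their own CBD during placebo and that extra CBD adds less than the first dose. The argument about other sleep aids assumes that use differs by phase. The whole conclusion is subject to what the consent form and call script say. This is a cheap improvement; it does not show that the trial will fail.

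**What to change.** 1. Extend criterion 18 to the treatment period with the wording criterion 19 already uses, "for at least one week prior to and for the duration of the study". Add non-study CBD, hemp and cannabis to it, and repeat the rule in 5.3 and 6.5.
2. Add two yes/no items to the daily text message: (a) any CBD, hemp or cannabis product other than the study capsules; (b) any other sleep aid or sleep-affecting medicine. Keep them separate, because the two exposures act on the contrast differently. Item (b) also records criterion 17 medicines without adding a new ban on them.
3. Tabulate each item by treatment phase.

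How nights with such use enter the primary analysis is a separate question and need not be settled here.

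The cost is wording in three sections, two items in a message participants have already agreed to answer daily (criterion 5), and one descriptive table. The downsides are slightly more daily burden and somewhat tighter limits for people with insomnia and no rescue medicine, in a trial that anticipates up to 33% dropout. If made as an amendment, the change needs IRB review and a decision on re-consent under the Statement of Compliance.
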